DLTs will only be assessed during the first 28 days in cycle 1 (See Section 6.1, Dose Limiting Toxicity Criteria, for DLT definition). Transient hypotension which may require IV fluids for management is an expected event that subjects may experience with ADXS11-001 infusions. Subjects with signs of cytokine release symptoms ≥Grade 3 (per CTCAE v 4.03) that persist for more than 24 hours despite symptomatic treatment, will be judged to have a DLT. Blood cultures will not be obtained on a routine basis but will be collected in subjects who have persistent fever 24 hours after the end of ADXS11-001 infusion. Subjects will receive a 7-day course of either oral 80 mg trimethoprim / 400 mg sulfamethoxazole once daily or 160 mg trimethoprim / 800 mg sulfamethoxazole (DS) 3 times over the course of the 7 days. Subjects with known allergy to sulfa drugs may receive ampicillin 500 mg 4 times daily for 7 days beginning on Day 4 (approximately 72) hours) after each study treatment infusion. A subject who experiences a fever (CTCAE Grade 1 or greater) 24 hours following the completion of ADXS11-001 infusion should be started on NSAIDS, hydration and other appropriate measures to treat the fever. In the event that the fever persists or worsens 48 hours following the completion of ADXS11-001 infusion then oral or broad spectrum IV antibiotics should be considered based on the subject's medical condition. If the fever remains unresponsive to oral/IV antibiotics 72 hours following the completion of the infusion then a blood culture should be obtained to evaluate for listeremia and determine the appropriate treatment course for the subject. Study cycles can be repeated at the RP2D (or less) for each subject until a discontinuation criterion is met. Criteria include documented disease progression, intolerable side effects not resolved with dose reduction or change in pre-medications, or the completion of 1 cycle of treatment post observation of complete response per RECIST 1.1 and immunerelated RECIST criteria (irCR).

Safety will be assessed by comparing treatment-related AEs, changes in physical examinations, vital sign measurements, and laboratory abnormalities.

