6.1 Dose Limiting Toxicity Criteria

DLT will be evaluated during the first 28 days of the first cycle during the dose escalation portion of the trial. All toxicities will be graded using CTCAE v 4.03. The occurrence of any of the following toxicities will be considered a DLT, if judged by the Investigator to be possibly, probably or definitely related to therapy. Treatment modifications for DLT are shown in Table 11.

Hematologic:

- 1. Grade 4 hematologic toxicity.
- 2. Febrile Neutropenia, defined as absolute neutrophil count (ANC) < 1000/mm³ with a single temperature of >38.3° C (101° F) or a sustained temperature of >38° C (100.4° F) for more than 1 hour.
- 3. Grade 3 thrombocytopenia lasting >72 hours.
- 4. Grade 4 thrombocytopenia.

Non-Hematologic:

1. ≥Grade 3 non-hematologic toxicity, (excluding nausea, vomiting and/or diarrhea lasting <3 days and reversible with medical intervention).

- 2. Grade 3 non hematologic laboratory values, (excluding transient Grade 3 laboratory value abnormalities, hematologic and non-hematologic, reversible within 5 days and without necessity for medical intervention).
- 3. Listeremia: positive blood cultures(s) along with persistent (for 72 hours post dose) symptoms consistent with listeremia (e.g., fever and muscle aches, often preceded by diarrhea or other gastrointestinal symptoms).
- 4. \(\geq \) Grade 3 flu-like symptoms or cytokine release symptoms that persist for >24 hours after study treatment administration despite symptomatic treatment.

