Hypotension	2 Moderate	 Fluids and 1 dose of pressor (e.g. 0.3 mg epinephrine IM) Increase monitoring of vital signs If hypotension persist for more than one hour consider low dose corticosteroids (e.g. hydrocortisone 100 mg IV over 30 seconds 	 Extend infusion time to 2 hours. Increase pretreatment IV fluids (e.g. 500 ml -1L normal saline) Incorporate Glucocorticoid- Hydrocortisone or equivalent- 50 mg, IV, as premedication
All other cytokine release symptoms (e.g. chills, rigors, fever, nausea, vomiting)	2	Appropriate supportive care measure	 Extend infusion time to 2 hours. Consider increasing doses of prophylactic medications
Hypotension	3 Severe	 Fluids, high dose pressors (e.g. Dopamine 10 μg/kg/min) +1 dose tocilizumab*(4mg/kg over 1 hour) If hypotension worsens or is unresponsive to above measures, administer corticosteroids If the subject's condition does not improve or stabilize within 24 hours of the tocilizumab dose, administration of a second dose of tocilizumab +/- corticosteroids should be considered. 	Discuss with Sponsor

Toxicity	NCI CTCAE Grade or Severity	Treatment	Modification for Subsequent infusions
All other cytokine release symptoms (e.g. chills, rigors, fever, nausea, vomiting)	3	Appropriate supportive care measures	 Extend infusion time to 2 hours. Consider increasing doses of prophylactic dose of NSAID, or antiemetic as appropriate
Hypotension/ Organ toxicity, mechanical ventilation	4 Life threatening	 Vigilant supportive care Fluids High dose pressors, Tocilizumab (4mg/kg over 1 hour) +/- corticosteroids (hydrocortisone 100 mg IV infused over 30 seconds administered every 2 hours until symptoms resolve to <grade 1)<="" li=""> </grade>	Permanently discontinue

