11.5 Management of Infusion Reactions

While there is some overlap between infusion reactions symptoms and cytokine release symptoms, infusion reactions symptoms typically occur during the infusion, while cytokine release symptoms typically occur after the infusion and are mediated by a different mechanism of action. Signs/symptoms of infusion reactions may include: allergic reaction/hypersensitivity (including drug fever); arthralgia (joint pain); bronchospasm; cough; dizziness; dyspnea (shortness of breath); fatigue (asthenia, lethargy, malaise); headache; hypertension; hypotension; myalgia (muscle pain); nausea; pruritic/itching; rash/ desquamation; rigors/chills; sweating (diaphoresis); tachycardia; tumor pain (onset or exacerbation of tumor pain due to treatment); urticaria (hives, welts, wheals); and vomiting.

Table 10 below shows the management guidelines for subjects who experience an infusion reaction associated with administration of ADXS11-001.

Table 10 Recommended Management Guidelines for Infusion Reactions

NCI CTCAE Grade	Management
Grade 1	
Mild reaction; infusion interruption not indicated; intervention not indicated	Increase monitoring of vital signs as medically indicated until the subject is deemed medically stable in the opinion of the Investigator.
Grade 2	
Requires infusion interruption but responds promptly to symptomatic treatment (e.g., antihistamines, NSAIDS, narcotics, IV fluids); prophylactic medications indicated for ≤24 hrs.	Stop Infusion and monitor symptoms. Additional appropriate medical therapy may include but is not limited to:
	the subject is deemed medically stable in the opinion of the Investigator. If symptoms resolve within one hour of stopping drug infusion, the infusion may be restarted at 50% of the original infusion rate. Otherwise dosing will be held until symptoms resolve and the subject should be premedicated for the next scheduled dose.
Grades 3 or 4	
Grade 3: Prolonged (i.e., not rapidly responsive to symptomatic medication and/or brief interruption of infusion); recurrence of symptoms following initial improvement; hospitalization indicated for other clinical sequelae (e.g., renal impairment, pulmonary infiltrates) Grade 4: Life-threatening; pressor or ventilatory support indicated	 Stop Infusion. Additional appropriate medical therapy may include but is not limited to:

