	6. Subjects who experience a Grade 4 reaction should be permanently discontinued from study. Subjects who experience a grade 3 reaction may be discontinued. Discussion with the Sponsor is recommended

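### Table 10 makes stopping optional after a Grade 3 infusion reaction, although Sections 6 and 11.6.2 require stopping when that reaction is a DLT

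*Combined protocol and SAP*

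**What the plan says.** **Stop rule.** Sections 6 and 11.6.2 carry the same paragraph. A subject with a DLT in the escalation part, or with a DLT-type event in any later cycle, is taken off study treatment. The only way back is a significant response (not defined), a lower dose level, and agreement between Investigator and Sponsor.

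**DLT definition.** Section 6.1 states that "DLT will be evaluated during the first 28 days of the first cycle during the dose escalation portion of the trial". Section 6 adds that "DLTs will only be assessed during the first 28 days in cycle 1". The event must be judged at least possibly related. Two non-hematologic items matter here, each applying at the stated grade or higher:
- Item 1: "Grade 3 non-hematologic toxicity, (excluding nausea, vomiting and/or diarrhea lasting <3 days and reversible with medical intervention".
- Item 4: "Grade 3 flu-like symptoms or cytokine release symptoms that persist for >24 hours after study treatment administration despite symptomatic treatment". Section 6 repeats this: subjects with such symptoms "that persist for more than 24 hours despite symptomatic treatment, will be judged to have a DLT".

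**Table 10 (Section 11.5).** A Grade 3 infusion reaction is defined by any of three features. The first is "Prolonged (i.e., not rapidly responsive to symptomatic medication and/or brief interruption of infusion"; the others are recurrence after initial improvement and a need for hospitalization. Item 6 of the Grade 3/4 cell says Grade 4 reactions should lead to permanent discontinuation. For Grade 3 it says "Subjects who experience a grade 3 reaction may be discontinued", with Sponsor discussion recommended.

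**Table 9 (Section 11.4.1).** For Grade 3 cytokine release symptoms other than hypotension, the column on subsequent infusions says to lengthen the infusion to 2 hours and "Consider increasing doses of prophylactic dose of NSAID, or antiemetic as appropriate". It gives no limit on duration.

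**Cross-reference.** Section 6.1 sends the reader to Table 11 for treatment modifications after a DLT.

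**The concern.** The same event can fall under two instructions. Section 11.6.2 says a DLT ends treatment unless the response exception applies. Table 10, which staff will open when a reaction happens, leaves the decision to the site and requires neither a response nor a lower dose level. In a multi-center trial, sites can be expected to resolve this differently.

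What is at stake is subject safety. A woman who has had a prolonged or recurrent reaction, or one needing hospitalization, could be given another infusion of a live attenuated bacterium when the protocol elsewhere requires her to stop.

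**Working it through.** There is no figure in the plan to reproduce. The check sets the texts side by side and then works out how many infusions are affected.

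**1. Is a Grade 3 infusion reaction a DLT?** Item 1 of Section 6.1 takes in related non-hematologic toxicity of Grade 3 or higher and excludes only short, reversible gastrointestinal symptoms. Infusion reactions are not excluded. So a related Grade 3 reaction that is more than brief nausea, vomiting or diarrhea is a DLT if it occurs in escalation within the window, and a DLT-type event if it occurs in a later cycle.

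**2. What follows from it?**
- Sections 6 and 11.6.2: stop, unless there is response, a lower dose level and agreement.
- Table 10 item 6: stopping is optional, and none of those conditions is attached.

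A site that re-doses complies with Table 10 and breaches Section 11.6.2.

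**3. Table 9.** Item 4 makes Grade 3 symptoms lasting more than 24 hours despite treatment a DLT. The Table 9 row covers Grade 3 symptoms of any duration and describes the next infusion. It does not mention DLTs, so this is a missing carve-out.

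**4. Does the pointer to Table 11 settle it?** No, for two reasons.
- The non-hematologic rows of Table 11 exclude cytokine release symptoms and DLTs, so these events have no row there.
- The Grade 4 hematologic row allows restart on recovery to Grade 1 or baseline, with discontinuation only if recovery takes more than 12 weeks. Related Grade 4 hematologic toxicity is itself a DLT (Section 6.1, hematologic item 1), which Section 11.6.2 says ends treatment.

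**5. Calendar for cycle 1.** Inputs: infusions on Day 1 of Weeks 1, 4, 7 and 10 (Section 6); ±7 days (Table 5 footnote), applied here to the nominal day of each later infusion; DLT window Days 1 to 28. Infusion day = 1 + 7 × (week − 1).
- Infusion 1: Day 1.
- Infusion 2: 1 + 7 × 3 = Day 22, range 15 to 29. On schedule, 28 − 22 + 1 = 7 days of the window remain.
- Infusion 3: 1 + 7 × 6 = Day 43, range 36 to 50, outside the window.
- Infusion 4: 1 + 7 × 9 = Day 64, range 57 to 71, outside the window.

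In cycle 1, then, the stop rule plainly reaches events after infusion 1, and events after infusion 2 if it is given by Day 28. Cycle-1 infusions left open by Table 10: 4 − 1 = 3 after a DLT at infusion 1, and 4 − 2 = 2 after a DLT at infusion 2. Under Section 11.6.2 the number is 0 unless the exception applies.

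**6. Could the exception explain re-dosing in cycle 1?** It needs a response. The first scheduled scan depends on the text read:
- Table 5 footnote, Week 12 ± 1 week: 1 + 7 × 11 = Day 78, range 71 to 85.
- Section 8.1 item 17, 12 weeks ± 1 week after the first infusion: 1 + 84 = Day 85, range 78 to 92.

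The latest infusion 3 is Day 50, so the earliest scan follows it by 71 − 50 = 21 days or 78 − 50 = 28 days. On either reading no scheduled scan could support the exception before infusion 2 or 3. Only on the first reading could a scan fall on the same day as the latest infusion 4 (Day 71).

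**The case against.** The best defence is that the texts can be read together. Tables 9 and 10 are headed as recommended guidelines and cover all subjects and cycles. Some Grade 3 reactions lie outside the stop rule (those judged unrelated) or not plainly within it (cycle-1 events after Day 28, cycle-1 events in the expansion cohort). Optional wording is needed for those. The mandatory rule is stated twice, and the DLT exclusion in Table 11, followed directly by Section 11.6.2, suggests that DLTs were meant as a separate category. A site that stops obeys every text. Table 12 also requires advance approval before rechallenge after a serious event that the product may have caused.

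Much of this is probably the intent, but no visible text limits the optional wording in Table 10 to non-DLT reactions. The Table 12 safeguard is partial: it covers serious or higher-risk rechallenge and refers back to the protocol's dose modification guidelines, which are where the conflict lies.

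The defence is stronger for Table 9. Section 11.4.1 describes these symptoms as lasting up to 24 hours, so the Grade 3 row has a natural population that item 4 does not make DLTs. A reader might infer that the row permits re-dosing after a DLT. It does not say so; it only fails to exclude the longer cases. Nor does the Grade 3 hypotension row authorise re-dosing, since it only calls for discussion with the Sponsor.

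**Conclusion.** The conflict in Table 10 holds. For a related Grade 3 infusion reaction that meets Section 6.1, stopping is optional in one place and required, with one narrow exception, in two others. The Table 9 gap is secondary.

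Size: at most 3 further cycle-1 infusions after a DLT at infusion 1 and at most 2 after infusion 2, among the 6 to 12 escalation subjects. In later cycles the question can arise at any of the 4 infusions of a repeat cycle. These are ceilings. The visible text gives no rate of Grade 3 infusion reactions, so expected numbers are not estimated.

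Two stronger readings are tempting but unsupported. One is that the conflict distorts the DLT count or the choice of RP2D. It does not, because DLTs are counted under Section 6.1 whatever happens at the next infusion. The other is that it covers every Grade 3 reaction in the trial. The stop rule does not plainly reach cycle-1 events after Day 28 or cycle-1 events in the expansion cohort, and nothing is claimed for them.

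The finding that no text sets precedence is limited to what can be read. Items 1 to 5 of Table 10's Grade 3/4 cell and most of Sections 11.2 and 11.3 are not visible. Item 6 of Table 10 is intact.

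**What to change.** Three wording changes:
1. Add to the Grade 3 rows of Tables 9 and 10: *applies only to events not meeting the DLT definition in Section 6.1; for DLTs, and DLT-type events in later cycles, Section 11.6.2 governs.*
2. In Section 6.1, change the pointer for all DLTs, hematologic and non-hematologic, from Table 11 to Section 11.6.2.
3. Add the same DLT exclusion to the Grade 4 hematologic row of Table 11. Otherwise that row still offers a restart that Section 11.6.2 does not.

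The cost is amendment text only, with no change to the DLT definition, data collection or procedures. The downside is that some subjects who might have been re-dosed at a site's discretion will stop. Whether item 1 also captures Grade 3 cytokine release that resolves within 24 hours affects DLT counting. That is for the sponsor to decide separately.

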11.5.1 Listeriosis and Listeria Infection - Identification and Management

A person with (wt) listeriosis usually presents with fever and muscle aches, sometimes preceded by diarrhea or other gastrointestinal symptoms. Almost everyone who is diagnosed with listeriosis has an "invasive" infection, in which the bacteria spread

beyond the gastrointestinal tract. The symptoms vary with the infected person. Pregnant women typically experience fever and other non-specific symptoms, such as fatigue and aches. However, infections during pregnancy can lead to miscarriage, stillbirth, premature delivery, or life-threatening infection of the newborn. In people other than pregnant women, symptoms can include headache, stiff neck, confusion, loss of balance, and convulsions in addition to fever and muscle aches. Listeriosis can present in different ways. In older adults and people with immunocompromising conditions, septicemia and meningitis are the most common clinical presentations.[24] Subjects may need immediate evaluation with a brain CT scan or MRI and a lumbar puncture with the analysis of spinal fluid to rule out meningitis.

For symptomatic subjects, diagnosis is confirmed only after isolation of *Lm* from a normally sterile site, such as blood or spinal fluid (in the setting of nervous system involvement), or amniotic fluid/placenta (in the setting of pregnancy). Stool samples are of limited use and are not recommended. *Lm* can be isolated readily on routine media, but care must be taken to distinguish this organism from other Gram-positive rods, particularly diphtheroids. Selective enrichment media improve rates of isolation from contaminated specimens. You can expect that the cultures will take approximately 1-2 days for growth. Importantly, a negative culture does not rule out infection in the presence of strong clinical suspicion. Serological tests are unreliable, and not recommended at the present time [24].

Listeriosis is treated with a wide range of antibiotics. In preclinical studies, wt-*Lm* and ADXS11-001 are susceptible to the lowest tested concentration of the following antimicrobial agents:

11.5.2 Management and Surveillance of Listeria during Study Participation

In the event a subject experiences a persistent fever lasting 72 hours after receiving study treatment then the oral antibiotic regimen will be replaced by broad spectrum IV antibiotic treatment. If symptoms consistent with sepsis occur close to ADXS11-001 administration or at any time after ADXS11-001 administration, immediate medical attention must be sought. A microbial culture will be taken to identify the agent of sepsis and antibiotic sensitivity testing should be performed to confirm susceptibility. An infectious disease consult should be obtained for further management of these subjects.

All subjects will receive a 6-month course of an oral antibiotic regimen as a prophylactic measure following the completion of the last dose of ADXS11-001 treatment or at the time of study discontinuation. This additional safety measure is intended to eradicate *Lm* from the body.

Lm surveillance monitoring will also be initiated following the completion of the last dose of ADXS11-001 treatment or at the time of study discontinuation. This monitoring

will include obtaining a blood sample for CBC, comprehensive metabolic panel (CMP), including CRP and ESR, and blood cultures for the detection of *Listeria*. Testing will be performed on all subjects who have received at least 1 dose of ADXS11-001 and occur every 3 months (±2 weeks) for 3 years.

Should a diagnosis of listeriosis be made at any point after treatment with ADXS11-001 and the 6-month course of oral antibiotics are completed, immediate and intensive IV antibiotic treatment (ampicillin +/- gentamycin or other IV antibiotic regimen as indicated) is required. An infectious disease consult should be obtained. Based on each individual subject's case and at the discretion of the treating physician, the removal of any foreign medical object that has been present since treatment with ADXS11-001 was initiated may be warranted. It is extremely important that the Investigator, his/her research staff, other healthcare providers involved in the care of the subject as well as each subject participating in this study are educated and made aware of the signs and symptoms of listeriosis and the potential for delayed listeremia/listeriosis. Educational materials for the Investigator, research staff, health care providers and subjects will be prepared and educational training performed.

11.6 ADXS11-001 Toxicities and Treatment

Please refer to Section 3.4.1 for summary information on the ADXS11-001 AE profile.

ADXS11-001 is a live attenuated bioengineered nonpathogenic strain of Lm, and one that is known to stimulate a strong innate immune response characterized by high levels of cytokine release from immune cells into the general circulation. This pattern of side effects is consistent with other immunotherapy agents.

The most likely AEs associated with ADXS11-001 are comprised primarily of individual flu-like symptoms (e.g., fever, chills, body ache, and fatigue) or cytokine release symptoms (e.g., headache, nausea, vomiting, tachycardia, shortness of breath, hypotension and rash). The symptoms usually present within 2-4 hours after the completion of infusions and are often mild to moderate and transient in nature or respond quickly to symptomatic treatment. In rare instances they may last up to 24 hours. No cumulative or delayed toxicity has been observed.

Less likely AE's include increase heart rate, low blood pressure, muscle aches, headaches, allergic reaction, changes in blood chemistry, changes in blood counts, and short term changes in liver function.

Rare but serious AEs include high fever and difficulty breathing and hypotension.

, ADXS11-001 has a tropism for the liver. Transient asymptomatic elevations of ALT and alkaline phosphatase were observed after dosing in the Phase 1 trial without prophylactic medication administration. For that reason, subjects with significant liver disease are excluded, and particular attention is to be paid to hepatic abnormalities.

Please reference the ADXS11-001 IB for complete information regarding AEs.

During the time the subjects are at the study site, the infusion line will be left in place to administer parenteral drugs, should that be necessary. As described in Section 11, subjects will be pretreated to minimize side effects of the study agent. The Investigator should observe the subjects for signs of inflammation and/or infection, including unremitting fever or vomiting, that require more intense therapy, and to treat them appropriately. All such treatments are to be listed on the eCRF.

